# Background

## *Epidemiology of miscarriage*

Miscarriage, also known as spontaneous pregnancy loss before the fetus reaches viability, is a common early pregnancy complication. One in five pregnancies miscarries, which equates to over 250,000 miscarriages a year and 38,349 hospital admissions in the UK between April 1st 2015 and March 31st 2016. Miscarriage can be devastating to women and couples trying to conceive. It is a significant source of physical and psychological morbidity for many women and couples, the effects of which can endure for many months. Yet for all the physical and mental sequelae and the economic costs, we have made little progress in treating this distressing condition.

Most miscarriages happen in the first 12 weeks of pregnancy because of sporadic chromosomal abnormalities. However, for women with recurrent miscarriages, there may be genetic factors such as parental chromosomal abnormalities, embryonic chromosomal abnormalities, as well as structural anatomical abnormalities such as congenital uterine malformations causing miscarriage. Other risk factors include endocrine disease such as diabetes, systemic and genital infections and thrombophilia such as Anti-Phospholipid Syndrome. The full list is recorded in appendix A for reference. However, despite very thorough investigation (full list of recommended investigations is outlined in Appendix B), a significant proportion of women with recurrent miscarriage will be labelled as unexplained and be left with no definitive answers, treatments or sometimes sadly, hope.

## *Tubal disease and its effect on reproductive outcomes*

*C. trachomatis* is the most common sexually transmitted infection in the UK. *C. trachomatis* often has no symptoms, but can have serious health consequences, including fallopian tube damage. Untreated *C. trachomatis* infection in pregnancy may increase the risk of miscarriage, preterm birth, low birth weight and stillbirth.

A severe form of tubal damage is when the tube is blocked and filled with fluid, a condition called hydrosalpinx. They are classically caused by ascending infections from the lower genital tract such as chlamydia, which cause pelvic inflammatory disease, causing the tubes to appear swollen and enlarged. Hydrosalpinx is associated with a dramatic reduction in the chances of a live birth with assisted reproductive techniques. This is explained by reduced implantation chances and increased pregnancy losses in the presence of a hydrosalpinx. It is therefore strongly recommended that hydrosalpinges are removed or treated by tubal surgery prior to IVF.

It has been suggested that hydrosalpinx may have a causative role in recurrent miscarriage. The biological rationale for this increase in pregnancy losses is not yet well understood. It has been postulated that the hydrosalpinx fluid may be embryotoxic as it can include micro-organisms, endotoxins, cytokines and free radicals causing oxidative stress. This fluid may therefore alter the endometrial receptivity causing a disturbed cytokine cascade, which impedes implantation. Additionally, as the fallopian tube is occluded distally, the hydrosalpinx fluid may drain into the endometrial cavity having a flushing effect on the developing embryo hindering implantation.

## Detection of tubal disease

Investigation of suspected tubal disease is currently recommended for women with subfertility by laparoscopy or hysterosalpingography (HSG). Women who are not known to have comorbidities (such as pelvic inflammatory disease, previous ectopic pregnancy or endometriosis) should be offered HSG to screen for tubal occlusion because this is a reliable test for ruling out tubal occlusion, and it is less invasive and makes more efficient use of resources than laparoscopy. A HSG involves the passage of a radio-opaque contrast media through the female cervix whilst simultaneously taking serial radiographs to examine the patency and free spill of the media into the abdominal cavity. It requires radiographers, specialist radiographic equipment and exposure to radiation. Furthermore, a HSG is performed in a radiology department and requires a radiologist to interpret them.

Where appropriate expertise is available, screening for tubal occlusion using hysterosalpingo-contrast-ultrasonography (HyCoSy) can be considered because it is an effective alternative to HSG for women who are not known to have comorbidities. A HyCoSy is an outpatient procedure which only requires a special contrast media and an USS machine which is usually present in most gynaecological out-patient departments. It is performed at the same time as a pelvic ultrasound, which is recommended for both women with subfertility or recurrent miscarriages. The contrast media is injected through the cervix and its flow into the uterus and out through the fallopian tubes is tracked in real time using the ultrasound machine to detect tubal patency and pathology. A HyCoSy is a standard investigation for fertility problems.

Laparoscopy is an invasive operative investigation where by a fibre optic camera inserted through the umbilicus is used to directly visualise the passage of dye through the fallopian tubes thereby confirming their patency and function. Women who are thought to have comorbidities should be offered laparoscopy and dye so that tubal and other pelvic pathology can be assessed and treated at the same time. Laparoscopy costs the NHS significantly more than HSG or HyCoSy and carries more risk. Costs associated with laparoscopy are in the form of theatre use and staffing, equipment used, recovery facilities and a ward bed.

In addition to the tubal investigations mentioned above, it is also necessary to identify whether women undergoing these investigations have concurrent genital tract infection before undertaking tubal assessment. Tests to diagnose genital *C. trachomatis* infections have evolved rapidly and nucleic acid amplification tests (NAAT), such as polymerase chain reaction (PCR) are now widely available. NAAT has been estimated to have a sensitivity of over 90% and a specificity of 99%, regardless of sampling from a cervical swab or by urine specimen. A screen for *C. trachomatis* infection is recommended before women undergo any form of uterine instrumentation.

## Rationale for this study

Miscarriage affects one in five pregnancies and little progress has been made in understanding and treating this distressing condition. *C. trachomatis* is the most common sexually transmitted infection in the UK. *C. trachomatis* infection can have serious health consequences, including fallopian tube damage. Untreated *C. trachomatis* infection and tubal damage have been associated with miscarriage and adverse pregnancy outcomes such as preterm birth, low birth weight and stillbirth. A cohort study is needed to establish the prevalence of tubal disease in women with recurrent miscarriages. HyCoSy will be performed to identify tubal disease and establish the magnitude of the problem in the

recurrent miscarriage population. The prognosis of tubal disease on miscarriage and other obstetric outcomes, and the role of medical interventions such as tubal surgery (to treat hydrosalpinx) on reducing miscarriage and adverse obstetric outcomes will also be studied.

## Objectives

1. Establish the prevalence of hydrosalpinx in the recurrent miscarriage population.
2. Establish the prognosis of women diagnosed with recurrent miscarriage with concurrent hydrosalpinx.
3. Explore the role of tubal surgery for improving reproductive outcomes in women with recurrent miscarriage population and hydrosalpinx.

## Study Design

This is a prospective observational cohort study.

## Population to be studied

Potential participants will be approached at the Tommy's recurrent miscarriage clinic held at the Birmingham Women's Hospital.

### Inclusion criteria

- Age 18-45
- Women diagnosed with recurrent miscarriage i.e. 2 or more miscarriages
- Ability to give informed consent

Such a wide inclusion criteria will enable a true assessment of the prevalence of hydrosalpinges in the recurrent miscarriage population.

### Exclusion criteria

- Allergy to contrast media used for Hysterosalpingo-contrast-sonogram
- Allergy to sonographic gel used for ultrasound scanning
- Anatomical anomaly meaning transvaginal ultrasound scan not possible
- Stenosed/occluded cervix meaning contrast media unable to be introduced via cervix
- Inability to give informed consent
- Pregnant at the time of recruitment
- Declined recruitment

### Identifying Participants

Patients will have been given the patient information leaflet prior to their appointment, when they are sent their appointment details letter.

All women presenting to the clinic will be screened for the eligibility criteria by the routine healthcare provider. They will then be approached by [name] or one of the members of the research team and offered recruitment into the study.

## Data to be collected and tests to be performed

- Genital infection screen – This is required as per national guidance prior to any uterine instrumentation to reduce the risk of subsequent pelvic inflammatory disease during

Hysterosalpingo-contrast-sonography. The self-taken vulvovaginal swab and one high vaginal swab will then be sent to the microbiology laboratory of the Birmingham Women's Pathology department and will undergo testing for active infection causing bacteria for example *C. Trachomatis*, *N. Gonorrhoea*, *C. Albicans* or bacterial vaginosis. These tests will be in the form of microscopy, culture and sensitivities, polymerase chain reaction and Nugent's scoring. The storage and testing these swabs will be managed in line the Human Tissue Act, 2004.

- To establish the first objective of prevalence, recruited patients will be screened with a Hysterosalpingo-contrast-sonogram (HyCoSy) for the presence or absence of hydrosalpinges.

## Outcomes to be measured

- To establish the second objective of prognosis of women with recurrent miscarriage and concurrent hydrosalpinges, pregnancy outcome data will be collected from both groups of patients (patients who screen positive and those who screen negative for hydrosalpinges). Specifically this will include:
  1. Biochemical pregnancy – a positive pregnancy test either on urine or serum pregnancy testing before ultrasound evidence of a gestational sac
  2. Clinical pregnancy – a pregnancy confirmed by evidence of a fetal heartbeat on ultrasound scan or using ultrasound parameters (ultrasound visualization of a gestational sac, embryonic pole with heartbeat).
  3. Pregnancy loss and at what gestation the pregnancy was lost – if unfortunately the patient suffered from a further miscarriage or still birth, the gestation in weeks of the loss will be noted
  4. Ectopic pregnancy – if a clinical pregnancy is seen on ultrasound scan but its location of implantation has taken place outside the uterine cavity, this is known as an ectopic pregnancy. Ectopic pregnancies are usually inside the fallopian tube although rarely they can be abdominal, ovarian or cervical.
  5. Live births – if fortunately a patient has a live birth this will be noted.
- To explore the role of tubal surgery, the same pregnancy outcomes listed above will be collected for the group of patients that were treated by their usual healthcare provider with surgery for their hydrosalpinges.

## Method of collection of data and outcomes

- The genital infection screen will be performed by taking a self-taken vulvovaginal swab and a high vaginal swab after written informed consent has been gained. The high vaginal swab will be taken by [name], a General Medical Council and Royal College of Obstetricians and Gynaecologists registered registrar who is fully competent in such a procedure.
- The presence or absence of hydrosalpinges will be noted at HyCoSy which will be performed after recruitment and written informed consent has been gained. A urine pregnancy test will also be performed prior to the HyCoSy to ensure the patient is not unknowingly already pregnant which would exclude them from the study. The HyCoSy and pregnancy test will be performed by [name], a General Medical Council and Royal College of Obstetricians and Gynaecologists registered registrar who is fully competent in such a procedure.
- The pregnancy outcome data listed above will be collected via a telephone consultation or email correspondence, conducted at 6 months and 12 months either post HyCoSy or post

treatment. Should the patient not recall all of the information needed, she will be consented to examine her hospital patient records. Should the patient have had treatment at a different hospital trust, she would also have been consented to collect the specific information needed directly from that particular hospital's patient records.

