## Dissemination of study results

The results of the study in terms of the prevalence of hydrosalpinges in the recurrent miscarriage population and the prognosis of women with recurrent miscarriage and concurrent hydrosalpinx will be disseminated to all participants via an email newsletter at the conclusion of the study. The results of comparing outcomes between patients who were treated for their hydrosalpinges versus those who were not, will be also be disseminated to all study participants and those who were not treated will be offered discussion about treatment after the conclusion of the study if treatment shows significant benefit.

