## Patient Journey

The patient will be sent the patient information leaflet at the same time as they receive the appointment letter thus ensuring sufficient time to read the written information related to the study before consent is taken. Written informed consent will be taken by good clinical practice trained research midwives or [name], a General Medical Council and Royal College of Obstetricians and Gynaecologists registered registrar who is fully competent at taking consent and is also good clinical practice trained.

If a patient consents to participation, they will have the swabs performed as detailed in the method of collection of data and outcomes section above. If the swabs show an infection this will be treated

as per the Birmingham Women's Hospital microbiology prescribing guidelines. At a subsequent appointment they will have a HyCoSy to detect the hydrosalpinges instead of their usual transvaginal pelvic ultrasound scan. A HyCoSy, as detailed in the background section above, incorporates a transvaginal ultrasound scan but is more detailed due to the use of contrast media to detect tubal and uterine pathology which may not be visible on normal transvaginal ultrasound. The result of which will be fed back to the patient and their usual clinician. They will then discuss with this clinician any treatment that maybe required.

If a hydrosalpinx is detected they will discuss with their usual clinician whether tubal surgery and what type would be appropriate. Surgery would then be carried out in the usual manner by the usual clinician. All patients would now be in one of three groups, those with no hydrosalpinx, those with a hydrosalpinx who did not have surgical treatment and those with a hydrosalpinx who did have surgical treatment of their hydrosalpinx. All three cohorts will then be followed up for 12 months as detailed in the method of collection of data and outcome section above. A pictorial representation of the patient journey is shown below in the study flow chart section.

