### Statistical Analysis

For the prevalence survey of hydrosalpinx in the recurrent miscarriage population data will be presented using descriptive statistics. We will examine the prevalence data within subgroups created from clinical characteristics for example age, body mass index, previous sexually transmitted infections to identify high risk groups for hydrosalpinx.

For the comparison of the cohorts we will report numbers of individuals at each stage of study e.g. numbers potentially eligible, examined for eligibility, confirmed eligible, included in the study, completing follow-up, and analysed. The reasons for non-participation at each stage will be described. We will also describe the characteristics of study participants (e.g. demographic, clinical) and potential confounders (e.g. age, body mass index.) We will indicate the number of participants with missing data for each variable of interest and compute data for missing covariates using maximum likelihood estimation. We will summarise follow-up time (e.g. average and total amount) and report numbers of outcome events over time for each cohort. We will report unadjusted relative risk estimates and, if applicable, confounder-adjusted estimates and their precision (e.g. at the 95% confidence interval). We will endeavour to translate estimates of relative risk into absolute risk for a meaningful time period. Subgroup analyses will be also performed according to the risk stratification described above.

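### Outcomes stop at 12 months with no follow-up of ongoing pregnancies, so most early losses but only part of the term live births are counted

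*Protocol*

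**What the plan says.** The Exclusion criteria rule out women "Pregnant at the time of recruitment", and Method of collection of data and outcomes adds a urine pregnancy test before HyCoSy. Outcomes are then gathered by telephone or email, "conducted at 6 months and 12 months either post HyCoSy or post" treatment. Hospital records are used only where the woman cannot recall what is needed, so they do not lengthen follow-up. Patient Journey gives the same horizon: "All three cohorts will then be followed up for 12 months".

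Outcomes to be measured lists biochemical pregnancy, clinical pregnancy, loss with its gestation, ectopic pregnancy and live birth. For the last it says only that "if fortunately a patient has a live birth this will be noted". There is no time limit and no entry for a pregnancy still ongoing. The same outcomes serve Objective 2 (prognosis) and Objective 3, "Explore the role of tubal surgery for improving reproductive outcomes".

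Statistical Analysis promises relative risks and to "report numbers of outcome events over time for each cohort", without stating the denominator. End of study definition expects the study to last three years.

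**The concern.** A pregnancy that ends early fits easily into 12 months from a non-pregnant start; one that goes to term fits only if it begins in the first few months. Losses and live births from the same set of conceptions are thus observed over very different windows. Two things are at stake for Objectives 2 and 3:

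- The level: a loss or live-birth proportion among pregnancies that have ended by month 12 would look worse than the truth in every cohort.
- The comparison: if one cohort conceives more slowly, fewer of its births fall before the cut-off.

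A difference in time to conception is plausible. The background says of poorer live-birth chances with assisted reproduction: "This is explained by reduced implantation chances and increased pregnancy losses in the presence of a hydrosalpinx". The treated-versus-untreated result also has a consequence, since "those who were not treated will be offered discussion about treatment after the conclusion of the study if treatment shows significant benefit". Contact times are fixed in the protocol, and an analysis plan cannot recover births that were never collected.

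**Working it through.** The protocol states no figure on this point, so there is none to reproduce.

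**Inputs from the protocol.** Last contact at 12 months; not pregnant at HyCoSy (for treated women I assume the same when their clock starts at treatment); 184 women analysed (Sample Size); three-year study.

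**Assumptions of this review.** Conception 14 days after the last menstrual period; 4.348 weeks per month; all women trying from time zero; constant monthly conception chance f; loss risk L, with losses at 8 weeks; first pregnancy only unless stated.

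**Step 1: windows.** Months from conception to event = (gestation − 2)/4.348. Latest conception that is counted = 12 minus this.

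| Event | Months from conception | Latest conception counted |
|---|---|---|
| Birth at 40 weeks | 38/4.348 = 8.74 | month 3.26 |
| Birth at 37 weeks | 35/4.348 = 8.05 | month 3.95 |
| Loss at 8 weeks | 6/4.348 = 1.38 | month 10.62 |

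This step needs no conception rate. No term birth can be seen at the 6-month contact. Preterm live births have a longer window (28 weeks: month 6.0).

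**Step 2: share counted.** With F(t) = 1 − (1 − f)^t, the share of live births from conceptions in the 12 months that is counted is F(window)/F(12).

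- 40 weeks: 0.335 at f = 5%, 0.405 at 10%, 0.555 at 20%.
- 37 weeks: 0.399, 0.474, 0.629.
- 8-week losses: F(10.62)/F(12) = 0.914, 0.938, 0.973.

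A simulation that let women conceive again after an early loss (f = 5-25%, L = 30-40%, retry after 0 or 1 month) gave 31-51% of live births counted (40 weeks) or 37-58% (37 weeks). Over the same f, the first-pregnancy shares are 34-63% and 40-70%, so they are the favourable case.

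**Step 3: loss among resolved pregnancies.** Share = L·F(10.62) / [L·F(10.62) + (1 − L)·F(window)].

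- f = 10%, L = 0.3, 40 weeks: 0.3 × 0.673 = 0.202; 0.7 × 0.291 = 0.204; 0.202/0.406 = 0.50.
- Same, 37 weeks: 0.202/(0.202 + 0.7 × 0.341) = 0.46.
- Over f = 5-20%: from 0.54 (5%, 40 weeks) to 0.40 (20%, 37 weeks).

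The assumed true value is 0.30 throughout.

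**Step 4: per-woman live-birth relative risk.** With equal L in two cohorts it cancels, leaving F₁(window)/F₂(window) as planned, against F₁(12)/F₂(12) if every pregnancy conceived in the 12 months were followed to its end (40-week births).

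| Monthly chance | As planned | All followed |
|---|---|---|
| 5% vs 10% | 0.154/0.291 = 0.53 | 0.460/0.718 = 0.64 |
| 10% vs 20% | 0.291/0.517 = 0.56 | 0.718/0.931 = 0.77 |
| Equal | 1.00 | 1.00 |

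**Step 5: workload and calendar.** Women with a recognised (5-week) ongoing pregnancy at month 12, per 184: 29.8 (f = 5%, L = 0.4, 37 weeks) to 56.4 (f = 15%, L = 0.3, 40 weeks); counting all conceived by month 12, up to 59.5. With reconception after an early loss, 34 to 80. A check 2-4 weeks after the due date would fall at latest between month 11.31 + 8.74 + 0.46 = 20.5 and month 12 + 8.74 + 0.92 = 21.7, which is 8.5-9.7 months after the present last contact.

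**The case against.** The strongest reply is that a fixed 12-month horizon is legitimate and stated consistently: *live birth within 12 months* would be measured correctly, and Statistical Analysis intends absolute risks over a meaningful period. A clinical pregnancy with no loss, ectopic pregnancy or birth recorded is ongoing by elimination. Early loss, the study's main interest, is well captured. The sizes above rest on assumed rates, and following every pregnancy to its end costs calendar time.

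Much of this stands. It limits the point to labelling, denominators and a modest extra check. But Outcomes to be measured does not define the outcome by that horizon. Elimination gives neither gestation nor outcome. Reporting events over time covers only events that were collected.

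A reader might go further and infer any of the following, none of which the documents support:

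- *The surgery comparison is biased in a known direction.* No section gives conception rates by cohort. The implantation finding concerns assisted reproduction, and its size and direction here are unknown.
- *Further follow-up would remove the timing effect.* It would not: 0.53 becomes 0.64, not 1. With equal conception rates there was no distortion of the per-woman ratio to remove.
- *The authors plan proportions among resolved pregnancies.* The denominator is not stated; the risk is that the plan leaves this open.

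**Conclusion.** The point holds, as something that should be fixed. Followed as written, the plan counts a term birth only if conceived by about month 3.3 (40 weeks) or 4.0 (37 weeks), against about month 10.6 for an 8-week loss. These cut-offs rest only on the protocol's contact times and the 14-day convention.

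The clearer harm is to the level: on the assumed rates, a true 30% loss risk would appear as about 46-50% among resolved first pregnancies at 10% per month, and 40-54% over 5-20% per month. The effect on the cohort comparison is conditional: the cut-off magnifies an existing difference in time to conception (0.53 instead of 0.64 at 5% versus 10% per month, 40-week births) and creates none by itself in the per-woman ratio.

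All sizes assume constant conception chances with every woman trying. Counts fall if some are not trying; the shares do not change. Objective 1 and the sample size for prevalence are untouched.

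**What to change.** In Outcomes to be measured, Method of collection of data and outcomes, and Patient Journey:

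1. Record *ongoing at x weeks* at the 12-month contact.
2. Name the fixed-horizon outcome *live birth within 12 months*, which every cohort can supply on equal terms.
3. State that loss and live-birth proportions will not be computed among resolved pregnancies only.
4. For women pregnant at 12 months, make one further telephone, email or record check after the due date where that date falls within the planned three years, and report the remainder as ongoing, by cohort.

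**Cost.** Items 1 to 3 cost one data item and some wording. Item 4 costs one extra contact, through channels already planned, for up to about 30-60 of 184 women on the assumed rates (first pregnancy only; more if women reconceive), and a check that consent covers it. If the three years run from the first clock start, pregnancies in women starting by about month 14.3-15.5 (36 − 21.7 to 36 − 20.5) could all be completed; later starters only in part.

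Extending the study by about 8.5-9.7 months so that every pregnancy reaches its outcome is optional. The documents do not show that it is necessary, and the investigators must weigh it.

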## Accrual and Analysis

### Sample Size

We will attempt to recruit approximately 203 patients. For a prevalence survey in a condition where the prevalence is unknown, but it is not expected to be higher than 25% for obtaining a 95% level of confidence and precision at 0.05 we have estimated that 184 patients are required. To account for up to a 10% level of attrition, 203 patients should be recruited.

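### Hospital records are named as a back-up for failed recall, which leaves no stated route to an outcome for a woman who cannot be reached at 6 or 12 months

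*Protocol*

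**What the plan says.** In the Protocol, section Method of collection of data and outcomes, the woman herself is the primary source: "The pregnancy outcome data listed above will be collected via a telephone consultation or email correspondence, conducted at 6 months and 12 months", timed from the HyCoSy or from treatment. The next sentence brings in a second source: "Should the patient not recall all of the information needed, she will be consented to examine her hospital patient records". For women treated elsewhere, it adds that "she would also have been consented to collect the specific information needed directly from that particular hospital's patient records".

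The Patient Journey section applies this to women without hydrosalpinx, with untreated hydrosalpinx and with surgically treated hydrosalpinx: "All three cohorts will then be followed up for 12 months".

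The Statistical Analysis section undertakes to report how many women finish follow-up, and "We will indicate the number of participants with missing data for each variable of interest". For the comparison of cohorts it plans the following: "We will report unadjusted relative risk estimates and, if applicable, confounder-adjusted estimates and their precision".

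The only stated allowance for loss is under Sample Size ("To account for up to a 10% level of attrition"), where the target rises from 184 to 203. No section describes repeat contact attempts, or a look at the records, for a woman who does not reply.

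**The concern.** The back-up source is tied to a failure of memory, and a memory can fail only in a woman who has answered. The women for whom a second source matters most, those who do not answer, are not mentioned.

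Objectives 2 (prognosis with hydrosalpinx) and 3 (role of tubal surgery) rest entirely on these pregnancy outcomes. The hydrosalpinx women are likely to be few, and they are split again by whether they had surgery. If the chance of being reached depends on the outcome, and does so differently between cohorts, the relative risks are distorted. The Dissemination section ties an offer to discuss treatment with untreated women to what the surgery comparison shows, so a distorted result could reach participants. Part of this missingness is avoidable, because the study already intends to use hospital records.

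**Working it through.** **1. Who has a route to an outcome under the text as written?**

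| Situation at 6 or 12 months | Stated route |
|---|---|
| Reached, recalls everything | Telephone or email |
| Reached, does not recall everything | Her hospital records |
| Reached, treated at another trust | That trust's records as well |
| Not reached | None stated |

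The sentence on other trusts adds a place to look. It does not add a circumstance in which to look.

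**2. The plan's own attrition figure.** 184 × 1.10 = 202.4, rounded up to 203, which is the stated target. (Dividing instead gives 184 / 0.90 = 204.4, so 205; the difference is immaterial here.) This allowance belongs to the prevalence survey, whose endpoint is read at the HyCoSy. It is not a forecast of outcome loss at 12 months, and the Protocol gives no such forecast.

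**3. Size of the hydrosalpinx group among 203 recruits, before the surgery split.** The 25% is the Protocol's ceiling; 10% and 5% are assumptions.

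- 25%: 203 × 0.25 = 50.75, about 51 women; one woman is 1/51, about 2 percentage points
- 10%: 203 × 0.10 = 20.3, about 20 women; one woman is 1/20 = 5 points
- 5%: 203 × 0.05 = 10.15, about 10 women; one woman is 1/10 = 10 points

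**4. Limits on what missing outcomes could do.** Let r be the risk among women reached and m the fraction not reached. The risk in the full group lies between (1 − m)r and (1 − m)r + m. Assume r = 30% in both cohorts, so that the observed relative risk is 1.0.

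| m (assumed) | Full-group risk | Relative risk |
|---|---|---|
| 10% | 27% to 37% | 0.27/0.37 = 0.73 to 0.37/0.27 = 1.37 |
| 20% | 24% to 44% | 0.24/0.44 = 0.55 to 0.44/0.24 = 1.83 |

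These are extremes: every missing woman has the event in one cohort and none does in the other. The width of the risk range is simply m. The table shows how far missing outcomes could move a result and is no estimate of bias.

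**5. Sampling error for comparison.** With 10% of 51 women missing, about 46 are reached. At r = 30% the 95% half-width is 1.96 × √(0.30 × 0.70 / 46) = 0.132, an interval about 26 points wide. With 18 of 20 reached it is 1.96 × √(0.30 × 0.70 / 18) = 0.212, about 42 points wide. At 10% non-response, sampling error is the larger uncertainty.

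**6. Workload of a wider trigger.** At 10% not reached, 203 × 0.10 = 20.3, about 20 women; at 20%, about 41. Some might need checking at both time points.

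**The case against.** The strongest reply is that the section gives one circumstance for using records and forbids no others, so a sensible team could look up a silent woman anyway. That is fair as to the wording: the text does not say 'only'. But a collection rule should not depend on the team going beyond it, and no other section supplies the missing step.

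It is also fair that the bias is not demonstrated. Nothing in the Protocol says which women will be harder to reach. If both recent loss and a new baby lower response, the effects could offset each other. Small numbers limit these comparisons more than 10% non-response would, and objective 3 is exploratory. This restricts the claim to avoidable missing outcomes with possible bias of unknown direction.

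Three stronger readings are tempting, and the documents do not support them:

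- *Record consent is sought only when recall fails.* The first sentence on records could be read that way, but the next ("she would also have been consented to collect the specific information needed directly from that particular hospital's patient records") points to consent given earlier, and the consent pages are not available for review. The timing is unclear; it is not shown to be wrong.
- *Missing outcomes are left without any analysis method.* The stated method does concern covariates, but handling of missing outcomes and sensitivity checks commonly sit in a statistical analysis plan, which is not at hand.
- *The covariate method is single-value filling.* The phrase "compute data for missing covariates using maximum likelihood estimation" is loose, but it names a likelihood method and does not say that one value is filled in and treated as observed.

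**Conclusion.** The point holds as a gap in the collection rule. The Protocol states no route to a pregnancy outcome for a woman who is not reached at 6 or 12 months, although it already plans to use sources that would often hold that outcome. Objectives 2 and 3 are affected; objective 1 is not, because prevalence is read at the HyCoSy.

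The size cannot be fixed from the documents. It depends on the unstated 12-month non-response, on the number of women with hydrosalpinx, and on whether being reached depends on outcome differently between cohorts. A reader might take the 10% attrition allowance as the expected loss and the limits in the working as the expected bias. Neither follows: the allowance belongs to the prevalence survey, and the limits are extremes. What can be said is that in groups of about 10 to 51 women, before the surgery split, a handful of missing outcomes matters. This is a worthwhile, inexpensive improvement and not a flaw that undermines the study.

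**What to change.** Amend Method of collection of data and outcomes so that the trigger for record review has two limbs: the woman cannot recall the information, or she has not withdrawn and could not be reached at the 6- or 12-month contact. In both cases the review should cover her hospital records and those of any other trust known to have treated her. State plainly that the consent covering this access is the one given at recruitment; if the recruitment form already contains it, only the wording of this section changes. Women who have withdrawn stay under the withdrawal terms and are not looked up.

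The cost is a modest number of look-ups by the existing team: about 20 women if non-response were 10%, about 41 if it were 20%, some perhaps at both time points. The gain is incomplete. A pregnancy known only from a home test may never reach a hospital record, and for a woman who cannot be contacted the team may not know which other trust to ask. It would therefore help to record the source of each outcome (woman or records), so that the three cohorts can be compared on how completely outcomes were obtained.
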